3.7 Secondary Effectiveness Analyses

The primary effectiveness analysis will be repeated for the 3, 6 month and 12 month time points on the PP population.

Changes from baseline will be evaluated at the 3, 6, 9 and 12 month time points, for the following effectiveness measures, also on the PP population:

- St. Mark's (Vaizey) Incontinence Severity Score
- FIQOL questionnaire subscales

PGI-I scores at 3, 6, 9 and 12 months (assessment not done at Baseline)

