1.6.2 LIFE Pivotal Study

The LIFE Study (Protocol CA003) was a multi-center, prospective, open label clinical trial conducted at six (6) centers in the United States. As with the prior studies, all IRBs approved the trial as an NSR investigation. Furthermore, FDA is aware that this and the prior feasibility studies were conducted as NSR investigations and did not object to this categorization. The objective of this pivotal trial was to evaluate the safety and effectiveness of the Eclipse System for the treatment of Fecal Incontinence (FI) in adult women.

A total of 200 female subjects aged 19 to 75 were enrolled in the study between August 2012 and October 2013. Subjects were required to experience ≥ 4 fecal incontinence episodes during a 2 week baseline diary assessment to qualify for participation. Sixty-one (61) subjects met all study eligibility criteria and entered the 1 month Treatment Period to make up the Intent to Treat Cohort. Fifty-six (56) subjects completed the 1 month Treatment Period without major protocol deviations to make up the Per Protocol Cohort.

The primary endpoint was the percent change in the number of episodes of FI experienced while wearing the Insert during the 2-week assessment period (Treatment Period) as compared to the baseline 2-week assessment period. Clinical effectiveness of the Eclipse System (study success) was defined as occurring when at least 40% of the Intent to Treat Cohort demonstrated at least a 50% decrease in the number of FI episodes (recorded in a 2-week patient diary) after 1 month of treatment with the device as compared to the number of FI episodes reported during the Screening Period.

Secondary endpoints were reduction in the number of incontinent days while wearing the device and adverse events. Other endpoints included symptom improvement measured by the Fecal Incontinence Quality of Life (FIQOL), Modified Manchester Health Questionnaire (MMHQ), and Patient Global Impression of Improvement (PGI-I).

At 1 month, 78.7% of the ITT Cohort (95% CI, 66-88%, $p < 0.0001$) met the success criterion; 85.7% (95% CI, 74-94%, $p < 0.0001$) met the success criterion in the Per Protocol analysis and 85.7% of participants considered their bowel symptoms "very much" or "much better". There was significant improvement in all FIQOL (all $p < 0.001$) and MMHQ (all $p \leq 0.007$) subscales.

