3.4 Hypotheses

The null hypothesis is that the proportion of treatment responders at 3 months is no more than 40%, and the alternative hypothesis is that the proportion of treatment responders at 3 months is more than 40%:

$$H_0: \pi \leq 0.40$$

$$H_A: \pi > 0.40$$

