3.5 Endpoints

The primary effectiveness endpoint is the proportion of treatment responders at the 3 month time point in the ITT population.

Secondary effectiveness endpoints are:

- The proportion of responders at the 3, 6 and 12 month time points in the PP population.
- The change from baseline in mean scores on subject-reported outcomes related to symptoms and quality of life as reported by St. Mark's (Vaizey) Incontinence Severity Score, and FIQOL at the 3, 6, 9 and 12 month time points
- PGI-I scores at the 3, 6, 9 and 12-month time points

The safety endpoint is the safety of the device, as assessed by the number of device-related (Eclipse System) adverse events and device –related serious adverse events, as adjudicated by the Clinical Events Committee (CEC).

Subjects who are screen failures will not be included in the effectiveness endpoint analysis. However, their data will be reviewed to understand reasons for screen failure. All subjects in whom the device was inserted, even if just for fitting, will be included in the safety analysis. For all screen fail subjects, the Investigator or designee will complete Case Report Forms related to the completed visits and a Study Exit Form.

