3.6 Primary Effectiveness Analysis

The primary effectiveness analysis is an exact binomial test to evaluate whether the observed response rate is significantly larger than 40% after the first 3 months of the Treatment Period. The analysis will be performed on the ITT population. Subjects who do not complete at least 10 days of diary data at the 3-month time point and who do not continue in the study will be classified as treatment non-responders.

The number and proportion of treatment responders, and its 95% confidence interval, using exact (Clopper-Pearson) confidence limits, will be presented. A p-value for the one-sided upper-tail test of whether the proportion is significantly larger than 0.40, will also be presented.

The null hypothesis will be rejected if a sufficient percentage of subjects exhibit treatment response at the 3 month time point.

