3.11 Power and Sample Size Considerations

Power calculations were performed based on the primary effectiveness analysis, which tests whether the fraction of treatment responders is significantly greater than 0.40 ($H_0: \pi \leq 0.40$ vs. $H_A: \pi > 0.40$) using a one-sided exact binomial test, based on significance $\alpha = 0.025$ and power $1 - \beta = 0.90$.

Based on the LIFE study, we anticipate an 85.6% success rate among study completers and conservatively estimate 21.3% dropout within 3 months, resulting in an estimated 67% response rate in this study. With as few as 40 subjects in the ITT cohort, the study has $\geq 90\%$ power to detect a response rate greater than 40%. Additional subjects, up to the maximum of 150 subjects, will be enrolled through a specified end date in order to provide a more robust analysis.

Withdrawal from the study during the Screening Period is estimated to be quite high due to the baseline diary completion and device fitting requirements. Subjects who are successfully fit with the Eclipse System and successfully complete the Screening Period will be eligible for treatment. Therefore, an estimated 160 to 600 subjects may be recruited into this study in order to achieve 40 to 150 subjects who successfully enter the Treatment Period.

We estimate the subject dropout rate between the start of the Treatment Period and the 12 month visit to be 33%, yielding approximately 25 to 100 subjects completing 12 months of study participation. In a 12 month study of non-surgical management of stress urinary incontinence the dropout rate over this same time period was approximately 36%.²⁹

4 Adverse Events

Investigators and the Sponsor will carefully track and report adverse events. Any subject who is exposed to the Eclipse System, including the Eclipse Insert, the Trial Insert or Sizers (has any Eclipse System device inserted into their vagina) will be included in the Safety Cohort and Safety Endpoint Analysis.

Adverse event definitions are provided in **Table 4**. Based on clinical experience to date the expectation is a very low risk of serious or unanticipated device-related adverse events.

Table 4. Adverse Event Categories

Term	Definition

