8 STATISTICAL ANALYSIS

8.1 General Considerations

Continuous data will be summarized using count (n) the number of non-missing values and mean, median, standard deviation, minimum and maximum as appropriate. The interquartile range (IQR) may also be reported as appropriate. Categorical data will be summarized using counts and frequencies. In general, means and medians will be presented to 1 more decimal place than collected, and standard deviations to 2 more decimal places. Where appropriate, p values will be presented to 4 decimal places.

A one-sided, 2.5% significance level will be used for the primary efficacy endpoint. All p-values, aside from those in the primary efficacy endpoint, are presented for descriptive purposes only. No adjustments will be made for multiple comparisons.

Recorded data may be presented in data listings, aside from cost utilization data which is evaluated under a separate analysis plan. If listed, enrolled subjects will be listed first, followed by screen failures, where appropriate.

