11.2.1 Treatment Response

The primary analysis will be repeated at the 6, and 12 month time points, based on the ITT population. Subjects with missing treatment response information at a time point will be considered non-responders, as described in Section 8.2.

The primary analysis will be repeated at the 3, 6, and 12 month time points, based on the PP population for those time points. Subjects with missing treatment response information at a time point are excluded from the analysis of the PP population at that time point, as described in Section 8.2.

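### The protocol's only 6- and 12-month response endpoint is per-protocol, but it is tested against a 40% bar set on all enrolled women; ITT response should carry the durability conclusion

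*Protocol*

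**What the plan says.** **The bar and its denominator.** Protocol 3.4: "The null hypothesis is that the proportion of treatment responders at 3 months is no more than 40" per cent. Protocol 3.5: "The primary effectiveness endpoint is the proportion of treatment responders at the 3 month time point in the ITT population". Protocol 3.2 defines responder and non-responder over enrolled women and counts fewer than 10 diary days as non-response for that period. SAP 8.2 does the same for ITT. The 40% figure also appears in the earlier LIFE study, where Protocol 1.6.2 defines success as "at least 40% of the Intent to Treat Cohort demonstrated at least a 50% decrease in the number of FI episodes".

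**The secondary response analysis.** Protocol 3.5 lists response at 3, 6 and 12 months in the PP population only, and Protocol 3.7 repeats the primary test there: "The primary effectiveness analysis will be repeated for the 3, 6 month and 12 month time points on the PP population". Neither section has an ITT response analysis at 6 or 12 months. In SAP 11.2.1, "Subjects with missing treatment response information at a time point are excluded from the analysis of the PP population at that time point".

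**What the SAP adds.** SAP 11.2.1 also repeats the test at 6 and 12 months on ITT, with missing counted as non-response. SAP 11 makes ITT the primary efficacy population and PP supportive. SAP 8.1 gives the 2.5% one-sided level to the primary endpoint and calls all other p-values descriptive. SAP 10 nevertheless states that nothing has changed from the protocol.

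**Two PP definitions.** Protocol 3.3 requires at least 10 diary days at every treatment time point. SAP 7.2 requires them only at the 3-month visit.

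**The concern.** The stated objective is durability at 3 and 12 months. Women enter the Treatment Period only after a 50% reduction on the Test Diary, so the ways to fail later are loss of response or leaving the study. The protocol's one later response endpoint removes those who left and then applies the bar meant for everyone.

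The plan itself separates the two rates: Protocol 3.11 gets its 67% by reducing an 85.6% completer rate for 21.3% dropout. By 12 months the gap is wider: "We estimate the subject dropout rate between the start of the Treatment Period and the 12 month visit to be 33" per cent. A report that follows the protocol could show a small 12-month PP p-value against 40% when response among all enrolled women is at or below 40%.

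**Working it through.** **Inputs.** Null 0.40 (Protocol 3.4). Exact one-sided binomial test (Protocol 3.6: "The primary effectiveness analysis is an exact binomial test to evaluate whether the observed response rate is significantly larger than 40" per cent). Level 0.025 (SAP 8.1). Completer response 85.6%, dropout 21.3% by 3 months and 33% by 12 months, N from 40 to 150, 12-month completers about 25 to 100 (Protocol 3.11).

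**The plan's own figures first.**
- Expected ITT response: 0.856 × (1 − 0.213) = 0.674, stated as 67%.
- At N=40 the smallest r with P(X ≥ r | 0.40) ≤ 0.025 is 23. The exact level is 0.0189 and the power at 0.67 is 0.924, so the stated power of at least 90% reproduces.
- Completers: 150 × 0.67 = 100.5 and 40 × 0.67 = 26.8, in line with the stated 100 and roughly in line with 25.

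**Shift in the rate.** If women who leave have no diary and count as ITT non-responders, the responders are the same women in both sets, so

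PP rate = ITT rate / (1 − dropout).

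At ITT 40% this gives 0.40/0.787 = 0.508 at 3 months and 0.40/0.67 = 0.597 at 12 months. The LIFE results show the same mechanism: 78.7% of 61 ITT and 85.7% of 56 PP both come to 48 responders (48/61 and 48/56).

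**Chance of rejecting 40%.** PP size is taken as Binomial(N, 1 − dropout), with the exact critical value for each realised size.

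| True ITT response | Time (dropout) | N | PP test | ITT test |
|---|---|---|---|---|
| 40% | 12 mo (33%) | 40 | 47.9% | 1.9% |
| 40% | 12 mo (33%) | 100 | 87.9% | 1.7% |
| 40% | 12 mo (33%) | 150 | 97.3% | 1.9% |
| 35% | 12 mo (33%) | 40 | 20.4% | 0.3% |
| 35% | 12 mo (33%) | 150 | 66.2% | 0.04% |
| 40% | 3 mo (21.3%) | 40 | 18.8% | 1.9% |
| 40% | 3 mo (21.3%) | 150 | 63.0% | 1.9% |

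With completer numbers fixed, the 12-month results at ITT 40% are 96.9% (n=100, critical value 51) and 44.6% (n=27, critical value 17).

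**Same trial, two thresholds.** With 150 enrolled and 100 completers, the PP test rejects from 51 responders, which is 51/150 = 34% of those enrolled. The ITT test needs 73, or 73/150 = 48.7%.

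**Limit on the 3-month rows.** They fit the SAP's PP set. Under Protocol 3.3 a woman who leaves after month 3 also drops out of the 3-month PP set, and the documents do not give enough to compute that rate.

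**The case against.** **The SAP already covers this.** A reader of Protocol 3.7 alone might infer that the whole plan tests later response only in completers. It does not. SAP 11.2.1 adds the ITT tests, which reject 1.9% of the time in the headline scenario, so the ITT result would sit beside the PP one. With PP supportive and its p-values descriptive, no confirmatory claim rests on the PP test. This stands, and it removes most of the weight. What it leaves is a protocol endpoint that the SAP does not replace and says it has not changed.

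**97% is not an error rate.** A reader might take it as a false-positive rate. If completers truly respond at 59.7%, rejecting 40% among completers is correct. The figure measures how far the PP question has moved from the ITT question.

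**There is precedent for 40% in PP.** Protocol 1.6.2 also reports a PP result against the LIFE success criterion, and 40% is the only threshold it states. That explains why the test is repeated; it does not make the bar mean the same thing on a smaller denominator.

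**The scenario is unfavourable.** If completers respond at the planned 85.6% with 33% dropout, 12-month ITT response is 0.856 × 0.67 = 57.4%. At N=150 the ITT test then rejects 98.7% of the time and the two analyses agree. At N=40 they still part: 55.9% for ITT against 99.9% for PP.

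**Conclusion.** The point holds as a mismatch between the protocol's secondary response endpoint and the bar used to judge it. At a true 12-month ITT response of 40% and 33% dropout, the PP test rejects between about 48% (N=40) and 97% (N=150) of the time, against 1.9% for ITT at both sizes. A PP rejection at 12 months is therefore weak evidence of durable response among all enrolled women.

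These figures assume that leavers have no diary and that nobody is removed from PP for other reasons, such as major deviations. The documents do not support saying that the trial's error rate is inflated, that the primary conclusion is affected, or that the plan lacks an ITT analysis at 6 and 12 months. What remains is that the protocol and SAP disagree on which population carries the later response result, SAP 10 does not record the difference, and PP itself has two definitions.

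**What to change.** 1. In Protocol 3.5 and 3.7, make ITT response with missing counted as non-response the secondary response endpoint at 6 and 12 months, matching SAP 11.2.1, and base the durability conclusion on it.
2. Report PP response as a number, proportion and Clopper-Pearson interval, labelled as among completers, always beside the ITT result, with no test against 40%. State that the interval is not to be read against 40%. Without that statement the conclusion returns by another route, because the lower limit clears 40% exactly when the exact test rejects (n=100: 0.408 at 51 responders, 0.398 at 50).
3. Do not substitute a PP null scaled up for dropout. It would rest on planned rather than observed dropout, and the documents give no 6-month dropout.
4. Use one PP definition in Protocol 3.3 and SAP 7.2.
5. Record the added ITT analyses in SAP 10.

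The cost is a wording change in both documents. No new data are needed, and the ITT analyses are already in the SAP. The sponsor loses the favourable PP p-values.

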3.8 Additional Analyses

The change from baseline in the average (mean) number of FI *episodes per week*, and percent change from baseline, will be evaluated at the 3, 6, and 12 month time points. Negative values represent a decrease in the number of episodes (i.e., improvement), while positive values represent an increase in the number of episodes.

The change from baseline in the average (mean) number of FI *days per week*, and percent change from baseline, will be evaluated at the 3, 6, and 12 month time points. Negative values represent a decrease in the number of days (i.e., improvement), while positive values represent an increase in the number of days.

A cost analysis comparing the Eclipse System to other available therapies will also be performed. This will be described in a separate Statistical Analysis Plan.

3.9 Subgroup Analyses

The primary and secondary analyses will be repeated on the subgroups of < 65 years of age and ≥ 65 years of age.

3.10 Safety Analyses

The number of overall adverse events will be summarized using the Medical Dictionary for Regulatory Activities (MedDRA) system organ class and preferred term and listings will be reviewed at regular intervals by the CEC. Device-related adverse events, and device-related serious adverse events occurring at each time point will be summarized. The CEC adjudicated AEs will be utilized in the safety endpoint analyses

3.11 Power and Sample Size Considerations

Power calculations were performed based on the primary effectiveness analysis, which tests whether the fraction of treatment responders is significantly greater than 0.40 ($H_0: \pi \leq 0.40$ vs. $H_A: \pi > 0.40$) using a one-sided exact binomial test, based on significance $\alpha = 0.025$ and power $1 - \beta = 0.90$.

Based on the LIFE study, we anticipate an 85.6% success rate among study completers and conservatively estimate 21.3% dropout within 3 months, resulting in an estimated 67% response rate in this study. With as few as 40 subjects in the ITT cohort, the study has $\geq 90\%$ power to detect a response rate greater than 40%. Additional subjects, up to the maximum of 150 subjects, will be enrolled through a specified end date in order to provide a more robust analysis.

Withdrawal from the study during the Screening Period is estimated to be quite high due to the baseline diary completion and device fitting requirements. Subjects who are successfully fit with the Eclipse System and successfully complete the Screening Period will be eligible for treatment. Therefore, an estimated 160 to 600 subjects may be recruited into this study in order to achieve 40 to 150 subjects who successfully enter the Treatment Period.

We estimate the subject dropout rate between the start of the Treatment Period and the 12 month visit to be 33%, yielding approximately 25 to 100 subjects completing 12 months of study participation. In a 12 month study of non-surgical management of stress urinary incontinence the dropout rate over this same time period was approximately 36%.²⁹

4 Adverse Events

Investigators and the Sponsor will carefully track and report adverse events. Any subject who is exposed to the Eclipse System, including the Eclipse Insert, the Trial Insert or Sizers (has any Eclipse System device inserted into their vagina) will be included in the Safety Cohort and Safety Endpoint Analysis.

Adverse event definitions are provided in **Table 4**. Based on clinical experience to date the expectation is a very low risk of serious or unanticipated device-related adverse events.

Table 4. Adverse Event Categories

Term	Definition
Adverse event (AE)	Any untoward medical occurrence, unintended disease or injury, or untoward clinical signs (including abnormal laboratory findings) in subjects, users or other persons, whether or not related to the investigational medical device. This definition includes events related to the study device and events related to any involved procedures.
Serious adverse event (SAE)	
Any AE that
 
 • led to a death, • led to a serious deterioration in the health of the subject that: 
 ○ resulted in a life-threatening illness or injury ○ resulted in a permanent impairment of a body structure or a body function ○ required hospitalization or prolongation of existing hospitalization* ○ resulted in medical or surgical intervention to prevent permanent impairment to body structure or function, or to prevent one of the other outcomes (e.g. bronchospasm requiring treatment in an emergency room ○ led to fetal distress, fetal death, a congenital abnormality, or birth defect 
Note that a planned hospitalization for a pre-existing condition, or a procedure required by the clinical investigational plan, without a serious deterioration in health, is not considered to be an SAE. Note also that continuation of permanent disability (e.g. failure of the Eclipse Insert to improve FI) is not considered an SAE.

²⁹ Richter, et al. non-surgical management of stress urinary incontinence: ambulatory treatments for leakage associated with stress (ATLAS) trial. *Clinical Trials* 2007; 4: 92-101.

Term	Definition
Unanticipated adverse device effect (UADE)	Any serious adverse effect on health or safety or any life-threatening problem or death caused by, or associated with, a device, if that effect, problem, or death was not previously identified in nature, severity, or degree of incidence in the investigational plan or application (including a supplementary plan or application), or any other unanticipated serious problem associated with a device that relates to the rights, safety, or welfare of subjects. ³⁰

* For purposes of defining a serious adverse event, hospitalization is defined as admission to the hospital for longer than 24 hours or prolongation of a hospital stay due to the adverse event.

4.1 Adverse Event Severity

The investigator will be asked to characterize the severity of each AE as mild, moderate or severe according to definitions provided in **Table 5**.

Table 5. Adverse Event Severities

Term	Definition
Mild	The AE is transient and easily tolerated by the subject.
Moderate	The AE causes the subject discomfort, interrupts the subject's usual activities and requires a visit to a healthcare practitioner.
Severe	The AE causes considerable interference with the subject's usual activities; may be incapacitating and may require hospitalization.

4.2 Adverse Event Association

The relationship of all AEs to the Eclipse System will be reported on the Case Report Forms by the site investigator according to the definitions provided in **Table 6**. Any devices associated with SAEs will be returned in order to facilitate product investigations. Devices associated with non-serious adverse events may also be returned, at the direction of the Sponsor, to assist with product investigations.

Table 6. Adverse Event Relationship to Device

Term	Definition
Definite	Adverse event whose timing is highly plausible for causality and which cannot be explained by other factors
Probable	Adverse event whose timing is reasonable for causality and is unlikely to be explained by other factors
Unlikely	Adverse event whose timing is unlikely for causality and which could be explained by other factors
Not related	Adverse event whose timing makes causality improbable and which could easily be explained by other factors
Unknown	Adverse event whose plausibility of timing cannot be judged or in which information regarding other factors does not exist

